##### 13.2.2 Statistical Design:

Based on the patient population in this study it is believed that the median PFS time in patients with pembrolizumab (MK-3475) alone will be approximately 9 months.[25] We seek to detect a 50% improvement on this (to 13.5 months) utilizing a design that has an attained type I error rate of 0.20. With 96 evaluable patients (48 randomized to each arm), a one-sided  $\alpha=0.20$  log rank test will have 80% power to detect a 33% decrease in the hazard of progression with SBRT + pembrolizumab (MK-3475) compared to pembrolizumab (MK-3475) alone, which corresponds to a 50% increase in the median PFS time. If after 75 events have been observed, the hazard ratio is greater than 0.837, the study will be declared unpromising.

Interim Analysis Decision Rules: The chosen design has one interim look for futility that will occur after the 38th event is observed. If, at this time, the hazard ratio is greater than 1.013 accrual will be suspended due to futility and the study will be declared unpromising.

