### 13.0 STATISTICAL CONSIDERATIONS

#### 13.1 Study Design

The study population in this randomized phase II trial are patients with advanced Merkel cell carcinoma. The trial is designed to compare Progression Free Survival (PFS) in patients that receive SBRT + pembrolizumab (MK-3475) compared to pembrolizumab (MK-3475) alone in non-radiated lesion(s). This trial implements a group sequential design with one interim analysis for futility. East v6 was utilized to create the statistical design described below.

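### Does the final cut-off of HR 0.837 at 75 events contradict the stated one-sided type I error of 0.20?

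*Combined protocol and SAP*

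**What the plan says.** Section 13.1 fixes the type of design: "This trial implements a group sequential design with one interim analysis for futility". Section 13.2.2 gives its operating characteristics and boundaries.

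- Type I error: the target effect is to be detected "utilizing a design that has an attained type I error rate of 0.20".
- Sample and test: "With 96 evaluable patients (48 randomized to each arm), a one-sided" log-rank test at α = 0.20 is named, and this "log rank test will have 80% power to detect a 33% decrease in the hazard of progression". The medians are 9 and 13.5 months.
- Interim look: "The chosen design has one interim look for futility that will occur after the 38th event is observed". If, at that look, "the hazard ratio is greater than 1.013 accrual will be suspended due to futility and the study will be declared unpromising".
- Final look: "If after 75 events have been observed, the hazard ratio is greater than 0.837, the study will be declared unpromising".

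Section 13.2.3 refers back to 13.2.2 for the main analysis and adds only Kaplan-Meier curves and medians. No section gives a p-value threshold for the final look, and the terms binding and non-binding do not appear.

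**The concern.** A reader who converts the final cut-off to a p-value gets 0.22, a few lines below a log-rank test described at α = 0.20. If the final p-value were compared with 0.20, the cut-off would be HR 0.823. A final hazard ratio between 0.823 and 0.837 would then pass the hazard-ratio rule and fail the test, right at the decision line for the primary endpoint.

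The 0.20 would also depend on the interim stop being followed. If the trial carried on after crossing the futility line, the final cut-off of 0.837 would carry a type I error of 0.2205. The plan would then have two competing final rules and an error rate about 2 points above the one it claims.

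**Working it through.** **Inputs**, all from section 13.2.2: 38 and 75 events; cut-offs HR 1.013 and HR 0.837; 1:1 allocation; target hazard ratio 9/13.5 = 0.667; one-sided α = 0.20; power 80%.

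**Model.** At d events the log-rank statistic is Z = ln(HR) × √(d/4), with variance 1. It is centred at 0 under the null and at ln(0.667) × √(d/4) under the alternative. The statistics at the two looks have correlation √(38/75) = 0.712.

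**Step 1: the final cut-off taken alone.** ln(0.837) × √(75/4) = −0.1779 × 4.330 = −0.770, so the one-sided p is 0.2205. Rounding of 0.837 moves this only between 0.2197 and 0.2213, so rounding does not explain the gap. A nominal 0.20 at 75 events needs HR = exp(−0.8416/4.330) = 0.823.

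**Step 2: the interim look.** ln(1.013) × √(38/4) = 0.0129 × 3.082 = 0.040. Under the null the chance of continuing is Φ(0.040) = 0.516, so the trial stops with probability 0.484. Under HR 0.667 the chance of continuing is Φ((0.0129 + 0.4055) × 3.082) = Φ(1.290) = 0.901, so it stops with probability 0.099.

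**Step 3: both looks together.** The trial succeeds only if the interim hazard ratio is at most 1.013 and the final one is at most 0.837. The bivariate normal probability of this is:

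- under HR 1: **0.199**. A simulation of 4 million draws gives 0.198.
- under HR 0.667: **0.802**. If the stated 33% reduction is read as HR 0.67, it is 0.796.

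These reproduce the plan's 0.20 and 80%. Solving for the final cut-off that gives exactly 0.2000 with this interim look yields HR 0.838, against the printed 0.837.

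**Step 4: the alternatives side by side.**

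| Final cut-off | Type I error, stop followed | Type I error, stop ignored | Power, stop followed | Power, stop ignored |
|---|---|---|---|---|
| HR 0.837 | 0.199 | 0.2205 | 80.2% | 83.8% |
| HR 0.823 | 0.182 | 0.200 | 78.7% | 82.0% |

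Only the first row with the stop followed matches both stated figures. A final test at nominal 0.20 matches one or neither: 0.182 and 78.7% with the stop, 0.200 and 82.0% without it.

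**Step 5: the event count.** A fixed design with no interim look would need 4 × (0.8416 + 0.8416)² / (ln 1.5)² = 68.9, so 69 events. The planned 75 fit a design enlarged to pay for the futility look, which again points to 0.20 and 80% as figures for the whole sequential procedure.

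**The case for a change.** The strongest opposing case concerns wording. The sentence naming the α = 0.20 log-rank test does not call that level overall, and no nominal level for the final look is printed. An analyst could run the log-rank test at 75 events and compare its p-value with 0.20. At HR 0.83 (ln 0.83 × 4.330 = −0.807, p about 0.21) that analyst would report a failed test where the hazard-ratio rule would not call the study unpromising. The interim action is also described as a suspension of accrual. Section 13.5 uses the same verb for adverse events, where accrual can re-open with approval from the monitoring board. On that reading the futility stop might be reversible, and since it is crossed 48% of the time under the null, the point would matter.

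Part of this stands: the section could have said that 0.20 is the overall level and that the final nominal level is about 0.22. The rest does not carry.

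- The α = 0.20 phrase sits in a statement of power, describes the design as a whole, and sets no threshold for the last look. The only final decision rule written down is the one on the hazard ratio.
- The futility sentence does not end at suspension. It goes on to a verdict on the study, and it gives no override and no route to re-opening. Section 13.5 does spell out such a route for its own rule, so the contrast favours reading the futility stop as final.

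**Conclusion.** The concern does not hold. In a group-sequential design with a futility stop that is followed, the nominal level at the final look may exceed the overall level. Here 0.2205 at the last look becomes 0.199 overall, with 80.2% power, in agreement with the plan's stated figures. HR 0.837 is the final boundary of the stated design and does not compete with it.

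The conclusion rests on two assumptions: the usual large-sample normal behaviour of the log-rank statistic with roughly equal event numbers per arm, and the futility rule being applied as written. If it were ignored, type I error would rise by about 2 points, to 0.2205; that would be a departure from the plan, not a flaw in it. Even if someone misread the final test as nominal 0.20, the trial would go to the final analysis and land between the two cut-offs with probability only 0.199 − 0.182 = about 1.7% under the null and 80.2% − 78.7% = about 1.5% under the alternative.

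Moving the cut-off to 0.823 would express a preference for a non-binding futility rule. With the stop followed, it would replace a boundary that meets 0.20 and 80% with one giving 0.182 and 78.7%.

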**13.2.3 Analysis Plan:**

The main analysis with regards to the primary endpoint is described above, in section 13.2.2. In addition to this Kaplan- Meier curves will be constructed and median PFS times will be calculated for each arm.

**13.3 Sample Size, Accrual time, and Study Duration****13.3.1 Sample Size**

The chosen design requires 75 events (progressions plus deaths without progressions) and will accrue 96 evaluable patients (48 to each arm) to attain these events. In order to account for patients that: (a) do not have any non-radiated lesions, (b) are deemed ineligible, (c) cancel study participation prior to receiving any randomized treatment, or (d) have a major protocol violation, we will plan to accrue an additional 4 patients making the maximum overall accrual N=100 patients.

**13.3.2 Accrual Rate and Study Duration:**

The disease sites applicable to this study have not yet been studied extensively within the Alliance. As such an accrual rate of 3 evaluable patients per month was estimated based on experience in the clinic. The study team believes that this rate will be on the low end of what is possible.

At this rate, the accrual phase of the trial will require ~32 months. Under the alternative hypothesis (i.e. that there is a PFS benefit for SBRT + pembrolizumab (MK-3475) compared to pembrolizumab (MK-3475) alone) the 75th event will occur at ~41 months. To account for data entry and cleaning, this means the primary endpoint analysis can occur approximately 45 months after the beginning of the trial, depending on the actual rate of observed events.

**13.3.3 Primary Endpoint Completion Date for ClinicalTrials.gov Reporting:**

For purpose of ClinicalTrail.gov reporting, the Primary Endpoint Completion Date (PECD) for this study is the time that the 75th event is observed on an evaluable patient. This will be approximately 45 months after the study has begun enrollment under the alternative hypothesis.

**13.4 Supplementary Analysis Plans****13.4.1 Secondary Endpoints**

**Progression Free Survival among all RECIST lesions:** This endpoint is the same as the primary endpoint, but includes both irradiated and non-radiated lesions. It is a time to event endpoint and will be evaluated using the Kaplan- Meier method. PFS time is defined as the number of days from randomization to either evidence of disease progression or death (without evidence of progression). Median PFS times will be calculated for each arm and a cox proportional hazards model will be constructed to determine if there is a PFS benefit for patients receiving SBRT + pembrolizumab (MK-3475) compared to pembrolizumab (MK-3475) alone.

**Overall Response Rate (OS):** A patient will be declared to have responded to therapy if they have at least a PR on 2 consecutive evaluations (i.e. the response is confirmed). Response rates will be calculated and compared across treatment arms utilizing a chi-square test.

**Progression Free Survival at 6 months (PFS6):** A patient will be declared a success for this endpoint if they remain on study and progression free at 6 months. The rates of success will be calculated and compared across treatment arms utilizing a chi-square test.

**Safety/Toxicity:** Maximum grade adverse events will be summarized by treatment arm in a tabular setting. This will be done overall and for the 3 month time period from date of registration.

**Local control of SBRT treated lesion:** The protocol irradiated tumors are considered to be controlled if they have no evidence of progression. No evidence of progression is defined as CR, PR, or SD. If the protocol irradiated tumor progresses the date of progression will be recorded. Local control of the protocol-irradiated tumor will be described using the Kaplan-Meier technique.

**Delivered radiation dose using cone-beam CT images:** These radiation doses will be summarized descriptively and compared to the planned dose.

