**Schema**  
1 Cycle = 21 Days

\* All sites have identified the metastasis to be irradiated in the event their patient is randomized to arm 2.

\*\* Radiation therapy will be administered to 1 cancer deposit concurrent with the first dose or started within the first cycle of pembrolizumab (MK-3475) administration. This cancer deposit to be irradiated will be defined prior to randomization and treatment per the guidelines in Section 7.1.

Treatment is to continue until disease progression or unacceptable adverse event for a maximum period of two years. Patients will be followed for 5 years or until death, whichever comes first.

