## 9.2 CTCAE Routine Reporting Requirements

In addition to the solicited adverse events listed in Section 9.1, the following table outlines the combinations of time points, grades and attributions of AEs that require routine reporting to the Alliance Statistics and Data Center. Questions about routine reporting should be directed to the Data Manager.

Combinations of CTCAE Grade & Attribution Required for Routine AE Data Submission on Case Report Forms (CRFs)

Attribution	Grade 1	Grade 2	Grade 3	Grade 4	Grade 5
Unrelated			a	a	a
Unlikely			a	a	a
Possible	a	a	a, b	a, b	a, b
Probable	a	a	a, b	a, b	a, b
Definite	a	a	a, b	a, b	a, b

- a) Adverse Events: Other CRF - Applies to AEs occurring between registration and within 30 days of the patient's last treatment date, or as part of the Clinical Follow-Up Phase.
- b) Adverse Events: Late CRF - Applies to AEs occurring greater than 30 days after the patient's last treatment date.

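### The overall adverse event table ignores observation time, which is longer in Arm 2 if SBRT delays progression, and the planned 3-month table covers only early events

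*Combined protocol and SAP*

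**What the plan says.** Section 13.4.1 (Safety/Toxicity) states: "Maximum grade adverse events will be summarized by treatment arm in a tabular setting. This will be done overall". The same sentence adds a second table restricted to the 3 months after registration. No between-arm test, person-time rate, time-to-first-event method or report of treatment duration is specified. These two tables are the only analysis given for secondary objective 2.2.4, the rate of high-grade AEs by organ system.

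Observation time is governed elsewhere:

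- Schema: "Treatment is to continue until disease progression or unacceptable adverse event for a maximum period of two years". Section 7.0 agrees.
- Section 9.2, main AE form: "Applies to AEs occurring between registration and within 30 days of the" last treatment date, and it also covers the clinical follow-up phase. A separate late form takes grade 3 to 5 events at least possibly related that arise more than 30 days after last treatment.
- Section 5.0, post-treatment footnote: AE assessment within 12 weeks of ending treatment, then every 6 months until progression, for at most 5 years from registration. After progression, withdrawal or removal, only survival is collected.
- Section 13.2.2: control median, "it is believed that the median PFS time in patients with pembrolizumab (MK-3475) alone will be approximately 9 months"; target, "We seek to detect a 50% improvement on this (to 13.5 months".

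**The concern.** How long a patient's AEs are observed depends on time to progression, the quantity the trial hopes to lengthen in Arm 2. Both arms receive the same pembrolizumab schedule. If SBRT works, Arm 2 patients stay on drug and under AE assessment longer, so at the same monthly risk more of them reach a given maximum grade. In a by-arm table that excess sits in the column where toxicity of adding SBRT would be looked for. If SBRT shortened PFS, the distortion would run the other way and could hide toxicity.

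The 3-month table does not settle this for later events. It starts at registration, while Section 7.0 allows treatment to begin up to 21 days later and SBRT to start within the 21-day first cycle. A patient at both limits has about 13 - 3 - 3 = 7 weeks of observation after the first fraction. Section 8.0 notes that AEs may appear several months after the last dose. Such events can show only in the overall table.

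**Working it through.** **Design figures first.** The documents give no AE exposure figure, so I checked the design that supplies the medians. With z = -ln(HR) x sqrt(events)/2, the boundaries in Section 13.2.2 are z = -0.040 (38 events, HR 1.013) and z = 0.770 (75 events, HR 0.837), with correlation sqrt(38/75) = 0.71. The bivariate normal gives one-sided alpha 0.199 and power 0.802 at HR 9/13.5 = 0.667. This matches the plan ("utilizing a design that has an attained type I error rate of 0.20"; "will have 80% power to detect a 33% decrease in the hazard of progression").

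**Inputs.** Medians 9 and 13.5 months, 48 per arm (13.2.2); 24-month treatment cap (Schema, 7.0); 30-day tail, taken as 1 month (9.2). Assumed: exponential PFS, treatment stops at progression, no earlier toxicity stops. Monthly hazards are ln2/9 = 0.0770 and ln2/13.5 = 0.0513.

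**Observation time.** Mean time to cap c is (1 - exp(-lambda c))/lambda.

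| Window | Arm 1 (months) | Arm 2 (months) | Ratio |
|---|---|---|---|
| First 3 months, ending at progression | 2.68 | 2.78 | 1.04 |
| 24-month cap | (1 - 0.1575)/0.0770 = 10.94 | (1 - 0.2916)/0.0513 = 13.80 | 1.26 |
| 24-month cap + 30 days | 11.94 | 14.80 | 1.24 |
| To progression, 60-month cap | 12.86 | 18.58 | 1.45 |

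With data cut-offs at 41 or 45 months (13.3.2) and uniform accrual over 32 months, the 24-month-cap ratio is 1.21 to 1.25. Following AEs to progression gives 1.24 to 1.30 at those cut-offs. About 1 - 2.68/10.94 = 76% of Arm 1's expected treatment time falls after month 3.

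**Crude proportions with identical hazards.** For constant AE hazard h and window min(PFS, 24) + 1, the proportion with an event is 1 - exp(-h) x [lambda/(lambda+h) x (1 - exp(-24(lambda+h))) + exp(-24(lambda+h))]. I set h to give an assumed Arm 1 rate and applied the same h to Arm 2. For 20%, h = 0.0197 and Arm 2 shows 24.2%; the standard error of the difference is sqrt(0.200 x 0.800/48 + 0.242 x 0.758/48) = 8.5 points. The early column confines the hazard to the first 6 months.

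| Arm 1 (assumed) | Arm 2, constant | Excess (points) | SE (points) | Arm 2, early | Excess (points) |
|---|---|---|---|---|---|
| 10% | 12.3% | 2.3 | 6.4 | 10.5% | 0.5 |
| 20% | 24.2% | 4.2 | 8.5 | 20.9% | 0.9 |
| 30% | 35.9% | 5.9 | 9.6 | 31.4% | 1.4 |
| 40% | 47.1% | 7.1 | 10.1 | 41.7% | 1.7 |

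In the 3-month table the constant-hazard artefact is about 0.1 to 0.2 points for Arm 1 overall rates of 20% to 40%.

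**Why one overall rate ratio is not the answer.** Take the early scenario without the tail: h = 0.0473 for 6 months, then zero. Incidence is h/(h+lambda) x (1 - exp(-6(h+lambda))): 20.0% and 21.4%. Person-time at risk is (1 - exp(-6(h+lambda)))/(h+lambda) + exp(-6h) x (exp(-6 lambda) - exp(-24 lambda))/lambda: 8.85 and 11.03 months. The rate ratio is (0.214/11.03)/(0.200/8.85) = 0.86, although the hazards are equal. Splitting only at 3 months gives 1.00 for the first period. After it, incidence is 0.0816 over 6.34 months in Arm 1 and 0.0914 over 8.43 months in Arm 2, a ratio of 0.84. The later period needs a further cut, or a hazard model that compares patients at the same time since start.

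**The case against.** The plan is not silent on a fixed window. Its 3-month table nearly equalises observation and is well placed for early SBRT toxicity, because radiation is three fractions started within the first cycle. That stands, and it limits the concern to later events.

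The plan describes and does not test. Section 13.4.1 names chi-square tests for response and 6-month PFS and a Cox model for PFS, but nothing for AEs. A crude table of what happened under each regimen as delivered is legitimate. That also stands. No decision rule uses the table; the stopping rule in 13.5 is separate and applies to each arm alone.

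The artefact is below one standard error at 48 per arm, and small if AEs come early. That is correct. It is still systematic, and it is largest when SBRT succeeds.

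A reader might infer three stronger things, and the documents support none of them:

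- That AE collection stops with treatment. Sections 5.0 and 9.2 continue it into follow-up, although scheduled assessments still end at progression, so the dependence on PFS remains.
- That Arm 2 will look materially more toxic. This depends on AE rates and a hazard shape that the documents do not give.
- That exposure-adjusted incidence alone repairs the comparison. It is unbiased only if the hazard is constant over time; otherwise longer low-risk time in Arm 2 dilutes early SBRT harm.

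**Conclusion.** The point holds as a modest gap in the safety analysis, not as an error that invalidates a planned comparison. For events after month 3, the only planned summary is a crude proportion whose observation time follows PFS. At the design medians Arm 2 is observed about 21% to 26% longer within the treatment window, and up to 45% longer if AE follow-up runs to progression without a data cut-off. With no true difference in hazard, the crude excess is about 2 to 7 points under a constant hazard and about 0.5 to 2 points if AEs fall in the first 6 months, for assumed Arm 1 rates of 10% to 40%.

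These sizes rest on exponential PFS, treatment ending at progression and no earlier stops. Section 12.1.2 allows treatment past RECIST progression until it is confirmed, and Section 8.0 has permanent discontinuations for toxicity, so actual windows will differ. The direction remains as long as time under AE observation rises with PFS.

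**What to change.** In Section 13.4.1, keep both planned tables as description and add, by arm:

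1. Treatment duration and AE observation time (median and total person-months), with the start and end of the AE window defined.
2. Time to first grade 3 or higher AE: a cause-specific hazard ratio with confidence interval, censoring at the end of the AE window. Alternatively, give person-time rates by period with confidence intervals. A split at 3 months is the minimum; a further cut, for example at 6 months, avoids the dilution shown above.
3. Cumulative incidence of first grade 3 or higher AE at fixed times (for example 3, 6 and 12 months), with end of the AE window without an event as a competing event. State that after the early months this still reflects time on treatment.

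Add one sentence that any conclusion on added SBRT toxicity will rest on item 2 read with item 3, and not on a single overall exposure-adjusted rate ratio.

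The cost is some SAP wording and a few extra tables. The inputs are AE timing (date, or cycle if that is all that is recorded) and treatment dates, with no extra patients or visits. Precision will be low at 48 per arm, so the intervals should be shown and the results read as descriptive.

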## 1.0 BACKGROUND

### 1.1 Merkel cell carcinoma background and role of PD1 blockade

Merkel cell carcinoma (MCC) is a rare but extremely aggressive cutaneous malignancy. Risk factors for the development of MCC include chronic ultraviolet light exposure as well as immunosuppression. [1, 2] Approximately 80-90% of MCC are associated with infection by the Merkel cell polyomomavirus which leads to oncogenic expression of viral proteins including the large and small T antigens [3-5]. Approximately 40% of MCC patients develop metastatic disease with a median overall survival of approximately 9.5 months [6]. Similar to other neuroendocrine cancers, standard treatment for metastatic MCC has historically included platinum based chemotherapy with radiation therapy reserved for palliation in appropriate symptomatic patients.[7]

However, given poor survival in metastatic MCC, novel treatment strategies are needed. One such strategy is using immune based therapies to treat metastatic MCC. These approaches are based on the viral etiology for a large fraction of MCC. Blockade of the PD1/L1 axis particularly has been an attractive target given the known association of PD-L1 expression in virally infected cells. Given that MCPyV-specific T cells are detected in up to 67% of MCC tumors [8], and approximately 55% of MCC tumor cells express PD-L1[9] there is a strong rationale for anti-PD-L1 therapy in MCC. Furthermore, MCPyV-negative tumors have higher mutation and neoantigen burden[3], which may be associated with higher response to PD-L1.

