### 2.2 Secondary objective(s)

- 2.2.1 To describe the PFS of SBRT + pembrolizumab (MK-3475) compared to pembrolizumab (MK-3475) alone across RECIST measurable (including both radiated and non-radiated) cancer deposits.
- 2.2.2 To describe the overall response rate of SBRT + pembrolizumab (MK-3475) compared to pembrolizumab (MK-3475) alone in both radiated and in non-radiated deposit(s).
- 2.2.3 To determine the PFS at 6 months of SBRT + pembrolizumab (MK-3475) compared to pembrolizumab (MK-3475) alone across all cancerous deposits by RECIST.
- 2.2.4 To determine the rate of grade >3-4 adverse events, by organ system, by CTCAEv5.0.

- 2.2.5 To determine the local control of SBRT treated tumors.
- 2.2.6 To calculate delivered radiation dose using cone-beam CT images collected on the radiation treatment table in the final treatment position.

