- \*\* Physical examination, adverse event assessments, labs and scans are required  $\leq 12$  weeks after the end of treatment; thereafter, every 6 months until disease progression for a maximum of 5 years following registration or more frequently as clinically indicated. See also [Section 12.0](#). At time of progression, withdrawal or removal, only survival information should be collected every 6 months for 5 years after registration.
- \*\*\* Radiation therapy will be administered to 1 cancer deposit concurrent with the first dose or started within the first cycle of pembrolizumab (MK-3475) administration. Eligibility must have been documented prior to administration of radiation.
- † Only required if there is evidence or suspected brain mets
- # All sites of known disease as clinically indicated.
- 1 To be completed after registration and prior to treatment (See Appendix I). This questionnaire is included on all Alliance trials in order to further study the relationship between these assessments and overall survival in a meta-analysis setting.
- 2 For women of childbearing potential (see [Section 3.2](#)). Must be done  $\leq 7$  days prior to registration.
- 3 Baseline scans can include either: 1) a CT, spiral CT, or MRI or 2) an FDG-PET scan and diagnostic CT performed with both IV and oral contrast, and the CT acquired with 5 mm or less slice thickness. Supporting documentation is to be submitted, per [Section 6.1](#). Response assessment should include assessment of all sites of disease and use the same imaging method as was used at baseline.
- A After Cycle 3 (prior to cycle 4) then every 9 weeks, (prior to the start of cycles 4, 7, 10, 13, 15, etc.).

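### Local control of the irradiated lesion is described by Kaplan-Meier with no rule for death, so one minus the curve gives net local failure, which is at or above the share of patients whose lesion progresses

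*Combined protocol and SAP*

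**What the plan says.** Objective 2.2.5 is "To determine the local control of SBRT treated tumors". Section 13.4.1 defines the endpoint at lesion level: "The protocol irradiated tumors are considered to be controlled if they have no evidence of progression", with complete response, partial response and stable disease all counting as control. The analysis is one sentence: "Local control of the protocol-irradiated tumor will be described using the Kaplan-Meier technique".

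No event or censoring rule is given for death, for progression at other sites, or for loss of lesion imaging. The same section does name death when it defines PFS over all lesions: "PFS time is defined as the number of days from randomization to either evidence of disease progression or death (without evidence of progression".

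Follow-up also matters. The Section 5.0 calendar footnote on post-treatment follow-up says: "At time of progression, withdrawal or removal, only survival information should be collected every 6 months for 5 years after registration". Sections 12.1.3 and 12.2.2 likewise refer to survival follow-up after the drug is discontinued or treatment stops for toxicity. Section 12.1.2 lets clinically well patients continue therapy past a first RECIST progression that is not yet confirmed, so for some patients scans would run on beyond it.

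**The concern.** A patient who has died can no longer have local progression, so death is a competing event. Because the definition counts progression only, and the neighbouring PFS definition adds death explicitly, the natural reading is that deaths with a controlled lesion are censored. Kaplan-Meier then treats those patients as if they would have gone on failing locally at the same rate as the survivors. If censoring is independent, the result is net local failure, meaning failure in a setting where nobody dies first. It is not the share of irradiated lesions that progress, which is how a reader of objective 2.2.5 is likely to take it.

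Counting death as an event would not settle the matter. The curve would then be local-progression-free survival, which does not fit the definition in Section 13.4.1.

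At stake is the interpretation of one descriptive secondary result. The primary PFS comparison is untouched.

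**Working it through.** The plan states no rate, sample size or precision for local control, so there is no figure to reproduce.

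**Inputs from the documents**
- 48 evaluable patients in the SBRT arm; median PFS of 9 months on control and 13.5 months under the alternative (Section 13.2.2).
- One survival figure, as background (Section 1.1): "Approximately 40% of MCC patients develop metastatic disease with a median overall survival of approximately 9.5 months".

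**Assumptions**
- Constant hazards, with local failure h = 0.01 per month (0.005 and 0.02 as a range).
- Median survival of 18, 24 or 36 months.
- The share of PFS events that are deaths is 5-30%.

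**1. Every lesion imaged until death.** With d = ln 2 / median survival:
- 1-KM(24) = 1 - exp(-24h) = 1 - exp(-0.24) = 21.3%.
- Cumulative incidence(24) = h/(h+d) × [1 - exp(-24(h+d))].

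| Median survival (months) | d | Cumulative incidence | Excess of 1-KM (points) |
|---|---|---|---|
| 9.5 (historical) | 0.0730 | 10.4% | 10.9 |
| 18 | 0.0385 | 14.2% | 7.2 |
| 24 | 0.0289 | 15.6% | 5.7 |
| 36 | 0.0193 | 17.2% | 4.1 |

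At h = 0.005, 1-KM is 11.3% against 7.4-9.1% for 18-36 months (5.4% at 9.5). At h = 0.02 it is 38.1% against 25.8-31.1% (19.2% at 9.5).

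**2. Lesion imaging stops at first progression elsewhere.** Only deaths before progression now compete. Let p = ln 2 / median PFS, which is 0.0770 at 9 months and 0.0513 at 13.5, and replace d by the death share of p. With h = 0.01:
- Smallest gap (13.5 months, 5% deaths): d = 0.0026, cumulative incidence 20.7%, excess 0.6 points.
- Largest gap (9 months, 30% deaths): d = 0.0231, cumulative incidence 16.6%, excess 4.8 points.

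Over assumed 12-month net failure of 5-30%, the same set-up gives an excess of 0.1-3.6 points at 12 months and 0.3-10.6 at 24 months.

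**3. Censoring at progression elsewhere is informative.** Step 2 takes local failure and progression elsewhere as independent. A simulation let them share a gamma frailty. It assumed median PFS 13.5 months, 15% of PFS events deaths, median survival after progression 12 months, and 12-month net failure of 20% at average frailty. It compared 1-KM, censored at progression elsewhere or death, with the true share of patients failing locally before death:

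| Frailty variance | 12 months: 1-KM vs true | 24 months: 1-KM vs true |
|---|---|---|
| 0 | 20.0% vs 18.4% | 36.1% vs 29.6% |
| 1 | 15.0% vs 15.5% | 23.0% vs 22.8% |

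With strong dependence the two errors roughly cancel, and at 12 months the sign reverses.

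**4. Precision.** Under step 2, the expected number still at risk at 24 months is 48 × exp(-24(h+p)), which is 5.9 at 9 months and 11.0 at 13.5. The large-sample Greenwood variance of the Kaplan-Meier estimate is S² × (h/48) × [exp(24(h+p)) - 1]/(h+p), with S = exp(-0.24) = 0.787. The standard errors are 0.102 and 0.084, so 95% intervals are about ±20 and ±16 points.

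**The case against.** **The plan never says deaths are censored.** True. It is an inference from the progression-only definition beside a PFS definition that names death. What the documents show for certain is a missing rule.

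**Net local control may be the quantity wanted.** The objective and definition are about the lesion, and Kaplan-Meier is a legitimate estimator of net control if censoring is independent. This stands: the error lies in reading the curve as the share of patients with local failure. The plan does not say which is meant, and independence is doubtful where censoring follows progression elsewhere.

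**High mortality is not shown for this trial.** A reader might infer from the 9.5-month figure that local failure would be overstated about twofold, 21% against 10%. The documents do not support that. The figure appears next to historical platinum chemotherapy, and no survival figure on pembrolizumab is given. A median survival of 9.5 months also cannot coexist with the 13.5-month median PFS targeted for the SBRT arm, since survival is never shorter than PFS.

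**Imaging until death conflicts with the calendar.** Also right. A reader might conclude that reported local control is bound to be too low. That direction is certain only for the death component; step 3 shows that informative censoring at progression elsewhere can offset it.

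**The gap lies within sampling error.** On step 4, yes at 24 months. But the interval would be centred on the net quantity, and naming the right one costs almost nothing.

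**Conclusion.** The point holds in limited form. With deaths censored, 1-KM is at or above the cumulative incidence of local progression computed from the same data, and the plan offers no competing-risk estimate and no censoring rule. The size cannot be fixed from the documents. At an assumed 1% per month it is about 4 to 7 points at 24 months for median survival of 18-36 months with imaging until death, and about 0.6 to 5 points if imaging ends at progression elsewhere and 5-30% of PFS events are deaths. In the second case the net direction against the true share is uncertain, and the unstated handling of progression elsewhere matters at least as much as the handling of death.

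The consequence is minor: one descriptive secondary endpoint, in one arm of 48 evaluable patients, with no test, threshold or decision attached.

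**What to change.** In Section 13.4.1, replace the Kaplan-Meier sentence with: *Local progression of the irradiated lesion will be described by the cumulative incidence function (Aalen-Johansen) with death without local progression as a competing event.*

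Then add:
- Patients are censored at the last assessment of the irradiated lesion when lesion imaging ends for progression elsewhere or discontinuation.
- A sensitivity analysis treats progression elsewhere as a competing event. It estimates local failure as the first event, which is observable under the current calendar without assuming independent censoring at progression elsewhere.
- Kaplan-Meier is kept as a supplement, labelled as net local control.

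The first addition is needed because Aalen-Johansen with death alone does not settle what happens when imaging stops. Censoring there still leaves possible informative censoring. Keeping patients at risk without scans would miss local failures.

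The cost is a few sentences of analysis text, with the same data and standard software. The drawback is a slightly less direct comparison with older Kaplan-Meier series, which the supplement covers.
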